- Number of days alive and free of respiratory failure at Day 28
- Number of days with respiratory failure up to Day 28
- Number of days hospitalized up to Day 28
- Number of days in ICU (length of stay) up to Day 90
- Number of days alive outside of hospital up to Day 28
- Number of days alive outside of hospital up to Day 90
- Pharmacokinetics in the study population at 100 mg QD

Exploratory Endpoints:

- See [Section 3.2.3](#)

Subject Population

- ≥18 years with reverse transcriptase polymerase chain reaction (RT-PCR) confirmed infection with severe acute respiratory syndrome coronavirus 2 (SARS-CoV-2)
- COVID-19 pneumonia (documented radiographically) requiring hospitalization; oxygen saturation level <94% on room air or subject requires supplemental oxygen.

Refer to [Section 5](#) for complete eligibility details.

Investigational Product (IP) Description:

Investigational Product (IP) is STI-5656 (Abivertinib maleate)

Planned Sample Size

Approximately 80 subjects will be enrolled in this study, 40 will be randomized to each of two treatment arms.

Treatment Arms

All subjects will receive current standard of care (SOC) treatments.

In this setting, subjects will receive one of two treatments up to Day 14 or until hospital discharge (if sooner):

Arm 1: STI-5656 (100 mg QD starting dose)

Arm 2: Placebo QD

Duration of Study

For subjects, the total duration of the study will be up to 94 days (up to 4 days for the screening period plus up to 14 days for treatment and up to 90 days from randomization for follow-up).

The length of the study will be approximately 7 months (4 months for enrollment plus up to 90 days study duration).

Study Design

This is a Phase 2, randomized, double blind, placebo-controlled, 2-arm multicenter study to assess the safety and efficacy of STI-5656 (capsule administered orally) in the setting of current standard of care (SOC) in subjects with RT-PCR confirmed SARS-CoV-2 (COVID-19) infection and pneumonia (documented radiographically) requiring hospitalization. Subjects must have oxygen saturation levels < 94% on room air or subject requires supplemental oxygen.

Eighty (80) subjects meeting eligibility criteria will receive SOC treatment and will be randomized at a 1:1 ratio to one of two treatment arms

- Arm 1: STI-5656
- Arm 2: Placebo

The starting dose of STI-5656 is 100 mg PO QD administered up to 14 days or until hospital discharge whichever is sooner. Placebo follows the same schedule.

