Subjects who discontinue at any time after randomization will not be replaced. There is no treatment crossover in this study.

Once subjects provide informed consent, they will have screening assessments performed (up to a 7-day screening window). Study Day 1 is the day of randomization. Subjects randomized should receive their first dose of STI-5656 or placebo on the day they are randomized (Day 1).

Subjects will be assessed daily while hospitalized. Subjects in both arms are assessed for adverse events and toxicities and all adverse events should be reported regardless of treatment arm assignment or causality.

PK samples will be collected from the first 20 subjects enrolled in this trial. For sampling time points please refer to the schedule of assessments.

Subjects will have an outpatient visit on Day 28 (for various study procedures) and a telephonic contact on Day 60 to collect any additional AEs and follow-up for unresolved AEs to resolution or to establishment of a new baseline.

SOC treatments will be collected in the electronic case report form (e-CRF) until hospital discharge. Continued outpatient treatment (concomitant medications) will be collected until Day 28. Any investigational medication received will be collected until Day 90.

Note: Investigational medicines other than STI-5656 are prohibited up to Day 28 or hospital discharge.

Discharged subjects will be contacted at Day 60 and Day 90 to collect survival, any experimental treatments and additional hospitalization information since the study hospital discharge.

[figure not shown]
Subjects should be encouraged to remain in the study even if Study Drug is discontinued (for any reason).

Statistical Design

An evaluable sample size of 40 subjects per group (treatment arm) will provide 80% power ($\alpha=0.05$, 2-sided) to detect a difference between groups in the number of subjects alive and free of respiratory failure at Day 28. This assumes that 95.7% of subjects who received STI-5656 plus SOC (group 1) and 70% of subjects who received only SOC (group 2) will be alive and free of respiratory failure at Day 28. This represents a treatment effect difference of approximately 26%.

All tests of significance will be assessed at alpha level=0.05, 2-sided.

Figure 1: Study Design

Schedule of Assessments (SOA)

See [Table 1](#) for SOA

Data Monitoring Committee

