¹²Record FiO₂ (and PaO₂) at the time of arterial blood gas sampling. If PaO₂ is not available, use SPO₂. Other respiratory status data to collect includes oxygen supplementation status: mechanical ventilation, face mask, nasal cannula or room air. Radiographic findings will also be collected.

¹³AEs will be collected from the time of informed consent to Day 60. Any ongoing AEs at Day 28 will be followed until resolution or stabilization.

¹⁴An 8-category ordinal scale of patient health status ranges: 0=no clinical or virological evidence of infection; 1=no limitation of activities; 2=limitation of activities; 3=hospitalized, no oxygen therapy; 4=oxygen by mask or nasal prongs; 5=non-invasive ventilation or high-flow oxygen; 6=intubation and mechanical ventilation; 7=ventilation + additional organ support – pressors, rapid response team (RRT), extracorporeal membrane oxygenation (ECMO); 8=death. See [Section 14.2](#) for form.

¹⁵STI-5656 or placebo administration up to Day 14 or hospital discharge, whichever is sooner for subjects in Treatment Arm 1. Study drug capsules should be taken orally with 200-250 mL of water following at least 2 hours of fasting.

¹⁶Samples will be collected from the first 20 subjects enrolled. Sampling timepoints are as follows: Day 1 (predose) and at 0.5, 1, 2, 4, 8, 12, postdose on dosing days 1 and 8.

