3.2.2. Secondary Endpoints

- Types, frequencies, and severities of AEs and the relationships of AEs to IP; includes serious adverse events SAEs
- Proportion of subjects alive and free of respiratory failure at Day 60
- Change in clinical status (on a 0-8-point ordinal scale²) of subject at Day 7, Day 14, and Day 28
- Proportion of subjects alive and discharged from ICU at Days 14 and 28

² 8-category ordinal scale of patient health status ranges: 0=no clinical or virological evidence of infection; 1=no limitation of activities; 2=limitation of activities; 3=hospitalized, no oxygen therapy; 4=oxygen by mask or nasal prongs; 5=non-invasive ventilation or high-flow oxygen; 6=intubation and mechanical ventilation; 7=ventilation + additional organ support – pressors, rapid response team (RRT), extracorporeal membrane oxygenation (ECMO); 8=death.

- Time from randomization to first occurrence of respiratory failure or death on study due to any cause up to Day 28
- Percent change from baseline in CRP at Days 3, 5, 7, 10, 14, 28
- Relative change from baseline in oxygenation index (PaO₂/FiO₂) up to Day 5
- All-cause mortality at Day 60 and Day 90
- Number of days alive and free of respiratory failure at Day 28
- Number of days with respiratory failure up to Day 28
- Number of days hospitalized up to Day 28
- Number of days in ICU (length of stay) up to Day 90
- Number of days alive outside of hospital up to Day 28
- Number of days alive outside of hospital up to Day 90
- To assess the pharmacokinetic profile in the study population

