4. INVESTIGATIONAL PLAN

4.1. Overall Study Design

This is a Phase 2, randomized, double-blind, placebo-controlled, 2-arm multicenter study to assess the safety and efficacy of oral STI-5656 (or placebo) in the setting of current SOC in subjects with RT-PCR confirmed SARS-CoV-2 infection and COVID-19 pneumonia (documented radiographically) requiring hospitalization. Subjects must have oxygen saturation levels <94% on room air or subject requires supplemental oxygen.

Eighty (80) subjects meeting eligibility criteria will be randomized at a 1:1 ratio to one of two treatment arms in addition to SOC treatments:

- Arm 1: STI-5656
- Arm 2: Placebo

The STI-5656 dose is 100 mg p.o. QD administered up to 14 days or until hospital discharge if sooner.

SOC treatments will be collected in the electronic case report form (e-CRF).

Subjects who discontinue at any time after randomization will not be replaced. There is no treatment crossover in this study.

Once subjects provide informed consent, they will have screening assessments performed (up to 4-day screening window). Study Day 1 is the day of randomization. Randomized Subjects should receive their first dose of Study Drug on Day 1.

Subjects will be assessed daily while hospitalized. Subjects in both arms are assessed for adverse events (AEs) and toxicities and all AEs should be reported regardless of treatment arm assignment or causality. Subjects will be contacted on Day 28 to collect any additional AEs and follow-up for unresolved AEs,

SOC treatments will be collected in the electronic case report form (e-CRF) until hospital discharge. Continued outpatient treatment (concomitant medications) will be collected until Day 28. Any investigational medication received will be collected until Day 90. Note: Investigational medicines other than STI-5656 are prohibited up to Day 28 or hospital discharge.

Discharged subjects will be contacted at Day 60 and 90 to ensure survival and collect any experimental treatments and additional hospitalization information since the study hospital discharge. Subjects on Treatment Arm 1 (STI-5656) should be encouraged to remain in the study even if Study Drug is discontinued (for any reason).

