## **1.0 INTRODUCTION OF THE STATISTICAL ANALYSIS PLAN**

The statistical analysis plan (SAP) is based on protocol STI-5656-2001 ‘A Phase 2, Randomized, Double-Blind, Placebo-Controlled Study of The Safety and Efficacy of Sti-5656 (Abivertinib Maleate) In Subjects Hospitalized Due to Covid-19’, V5.0 dated 07Dec2020. It details the methodology to be used in analyzing the data and outlines the specifications in the Tables, Figures and Listings (TFLs) for data to be included for executing the final statistical analyses for this study.

PK analysis is not included in this plan.

The analyses specified in this document supersede any high-level analysis plan described in the protocol.

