Chemistry: performed locally. 14-analyte complete metabolic panel (CMP): Albumin, alkaline phosphatase (ALP), alanine aminotransferase (ALT), aspartate aminotransferase (AST), bicarbonate, total bilirubin (TBIL), blood urea nitrogen (BUN), calcium, chloride, creatinine, glucose, potassium, sodium, total protein, D-dimer, fibrinogen.

 Cytokines include TNF $\alpha$ , IFN $\gamma$ , IL-6, IL-1 $\beta$ , IL-7, IL-8, IL-10, IL-12, IL-17, IL-18, IP 10, VEGF-A

 Record FiO2 (and PaO2) at the time of arterial blood gas sampling. If PaO2 is not available, use SpO2. Other respiratory status data to collect includes oxygen supplementation status: mechanical ventilation, face mask, nasal cannula or room air. Radiographic findings will also be collected.

 AEs will be collected from the time of informed consent to Day 60. Any ongoing AEs at Day 28 will be followed until resolution or stabilization.

 An 8-category ordinal scale of patient health status ranges: 0=no clinical or virological evidence of infection; 1=no limitation of activities; 2=limitation of activities; 3=hospitalized, no oxygen therapy; 4=oxygen by mask or nasal prongs; 5=non-invasive ventilation or high-flow oxygen; 6=intubation and mechanical ventilation; 7=ventilation + additional organ support – pressors, rapid response team (RRT), extracorporeal membrane oxygenation (ECMO); 8=death. See Section 18.2 for form.

 STI-5656 or placebo administration up to Day 14 or hospital discharge, whichever is sooner for subjects in Treatment Arm 1. Study drug capsules should be taken orally with 200-250 mL of water following at least 2 hours of fasting.

 Samples will be collected from the first 20 subjects enrolled. Sampling timepoints are as follows: Day 1 (predose) and at 0.5, 1, 2, 4, 8, 12, postdose on dosing days 1 and 8.

CONFIDENTIAL

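### PK sampling has no Day 8 predose draw and stops 12 h into a 24 h dosing interval, so steady-state trough and AUC0-24 are extrapolated rather than observed

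*Protocol*

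**What the plan says.** The sampling times stand in one place in each document: footnote 16 of the Schedule of Assessments in Protocol section 2, and the same footnote in SAP section 12.1. The protocol wording is "Sampling timepoints are as follows: Day 1 (predose) and at 0.5, 1, 2, 4, 8, 12, postdose on dosing days 1 and 8"; the SAP repeats "Day 1 (predose) and at 0.5, 1, 2, 4, 8, 12, postdose on dosing days 1 and 8". The only predose sample is on Day 1. No section lists a Day 8 predose sample or a 24 h sample. The unit is not printed, and hours is the natural reading. The PK row of the table also marks the Screening column, although no screening time is listed.

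The dosing interval comes from Protocol section 4.1: "The STI-5656 dose is 100 mg p.o. QD administered up to 14 days or until hospital discharge if sooner". Section 7.1 of the protocol gives a different daily dose and capsule count from sections 4.1 and 6.2. Those passages must be reconciled, but all of them are once daily, so the 24 h interval is unaffected.

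PK is a secondary objective and a secondary endpoint. The synopsis has "Pharmacokinetics in the study population at 100 mg QD" and section 3.2.2 has "To assess the pharmacokinetic profile in the study population". No PK parameter is named. On the subset, the synopsis says "PK samples will be collected from the first 20 subjects enrolled in this trial". The SAP introduction says "PK analysis is not included in this plan".

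**The concern.** The single predose sample is taken before any drug has been given, so it carries no information about trough. On Day 8 the profile starts at 0.5 h, after an unmeasured concentration left by seven earlier doses, and stops halfway through the interval. The steady-state trough is therefore not observed, and AUC0-24 is not observed on either PK day. Both have to be extrapolated from the last few points, and neither document supplied here prespecifies a rule or model for doing so.

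What is at stake is how well a secondary objective is described in few subjects. The first 20 enrolled at 1:1 give about 10 on active drug. Fewer will have a Day 8 profile, because dosing stops at discharge. Samples not drawn in these subjects cannot be recovered later.

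**Working it through.** The documents state no AUC, trough, half-life or PK sample-size basis, so there is no figure to reproduce.

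**Inputs from the documents.** Postdose samples at 0.5, 1, 2, 4, 8 and 12 h on Days 1 and 8; interval 24 h; 20 PK subjects at 1:1.

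**Assumptions.** One-compartment oral model; half-life h from 3 to 24 h, with k = ln 2 / h; absorption rate ka 0.5 to 1.0 per h; log-normal error of 15% per sample, covering assay and sampling together.

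**Time not sampled.** (24 − 12)/24 = 50% of the interval.

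**AUC not sampled.** At steady state the share of AUC0-24 in 12–24 h is [ka·f(k) − k·f(ka)]/(ka − k), where f(x) = e^(−12x)/(1 + e^(−12x)). Example for h = 12 and ka = 1.0: k = 0.0578, f(k) = 0.5/1.5 = 0.333, f(ka) ≈ 0, and the share is 0.333/0.942 = 35.4%.

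**Trough bias.** The log-linear slope is fitted through the true 4, 8 and 12 h values at dose 8 and run from the 12 h value to 24 h. If absorption is still contributing at 4–12 h, the slope is too shallow and the trough comes out too high.

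**Accumulation.** The Day 8 to Day 1 ratio of AUC over 0.5–12 h is compared with the true AUC0-24 ratio.

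| Half-life | AUC share in 12–24 h, Day 8 (ka 1.0 to 0.5) | Extrapolated/true trough, no error (ka 1.0; 0.5) | Ratio of AUC0.5-12 | Ratio of AUC0-24 |
|---|---|---|---|---|
| 3 h | 8–11% | 1.07; 1.69 | 1.00–1.01 | 1.01 |
| 6 h | 23–26% | 1.04; 1.37 | 1.07–1.09 | 1.08–1.09 |
| 12 h | 35–38% | 1.03; 1.22 | 1.36–1.41 | 1.36–1.39 |
| 24 h | 43–44% | 1.02; 1.12 | 2.06–2.18 | 2.05–2.12 |

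**Error in one subject's trough (5th to 95th percentile).**

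- Three points: ln C24 = ln C12 + 12 × (ln C12 − ln C4)/8 = 2.5 ln C12 − 1.5 ln C4. The SD is 0.15 × √(2.5² + 1.5²) = 0.437, and exp(±1.645 × 0.437) = 0.49 to 2.05. Multiplying by the biases for 6–24 h gives a lower end of 0.49 × 1.02 = 0.50 and an upper end of 2.05 × 1.37 = 2.8.
- Measured predose sample: exp(±1.645 × 0.15) = 0.78 to 1.28.

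**Error in one subject's Day 8 AUC0-24.** By simulation with the same 15% error, using the three-point extrapolation, the 5th to 95th percentile ranges relative to truth are 0.89–1.22 at a 6 h half-life, 0.86–1.30 at 12 h and 0.83–1.33 at 24 h. With a measured Day 8 predose sample serving as both C0 and C24 the range is about 0.89–1.13. For the geometric mean of 10 subjects, the extrapolated AUC0-24 ranges over 0.95–1.12.

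**Check of the swap.** After seven doses, accumulation at a 24 h half-life is 1 − 2^(−168/24) = 99.2% complete, and more at shorter half-lives, so C0 can stand for C24 on Day 8 if doses were regular. Without assay error, trapezoidal AUC0-24 from predose, 1, 2, 4, 8 and 12 h, closed with C24 = C0, is within 5% of truth at every half-life from 3 to 24 h.

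**Subjects.** 20 × 1/2 = 10 expected on active drug. Under simple 1:1 allocation, which is an assumption, the chance of 7 or fewer is 13%.

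**The case against.** The strongest reply is that no stated endpoint is breached. The documents name neither trough, AUC0-24 nor accumulation, and PK analysis lies outside the SAP, so a population model could be planned elsewhere. The half-life is unknown, and if it is short the unsampled span holds little exposure. The group-level AUC0-24 above is tolerable even with extrapolation. The footnote is also loosely drafted, so a clarification might be all that is needed.

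Most of this stands, and it sets the size of the point. It does not remove it. A model would have no data beyond 12 h and no Day 8 predose value to anchor the trough, so the result would lean on the model's assumptions. The trough stays poorly determined in the individual subject across the whole range, and slow absorption biases it upward. At a 3 h half-life with ka 0.5 per h, where the AUC share is small, that bias is largest (1.69). As for drafting, the footnote attaches the predose sample to Day 1 only, and reading it as both days is not supported by its wording.

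A reader might go further and infer that accumulation cannot be measured. The documents do not support that: the six postdose times are the same on Days 1 and 8, so Cmax and partial-AUC ratios can be computed, and the partial-AUC ratio tracks the true ratio closely. Only accumulation based on trough or on AUC0-24 is lost. A reader might also take half the interval to mean half the exposure; the AUC share is below 50% in every case examined. Finally, extrapolating from the 8 and 12 h points alone gives a range of about 0.29 to 3.4 times truth (SD 0.15 × √(4² + 3²) = 0.75), but that is the worst case for one subject's trough, not a measure of the schedule as a whole.

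**Conclusion.** The point holds as a gap against the general aim of describing the PK profile at once-daily dosing. Steady-state trough is the main loss: one subject's extrapolated value is uncertain by about a factor of two or more in either direction, where a measured one would be within about a quarter. AUC0-24 becomes an extrapolated quantity with moderate error, and accumulation remains assessable.

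These sizes rest on an assumed one-compartment model, absorption rate, half-life range and 15% error, none of which the documents give. That no sample falls after 12 h or before the Day 8 dose does not depend on them, apart from reading the unit as hours. The primary endpoint, type I error and power are untouched. It is a minor, inexpensive improvement.

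**What to change.** In footnote 16 of Protocol Table 1 and SAP Appendix 1, replace the Day 8 0.5 h sample with a Day 8 predose sample and print the unit. Use the predose value as the observed trough and as C0. Use it as C24 only where the earlier doses were taken regularly, so that steady state can be assumed. A 24 h sample after the Day 8 dose would avoid that assumption, at the price of one extra draw.

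Optionally, add a PK tube to a routine Day 2 draw taken before the Day 2 dose. That supplies the missing 24 h point for Day 1 AUC0-24.

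The swap leaves the number of PK draws unchanged, and subjects are inpatients with daily blood sampling. The cost is footnote wording in an amendment and less detail on early absorption on Day 8, which the Day 1 profile still provides. The change helps only subjects not yet sampled. For any already sampled, trough and AUC0-24 should be reported as extrapolated, with the method stated.

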3. STUDY OBJECTIVES AND ENDPOINTS

3.1. Objectives

3.1.1. Primary Objective

To assess the efficacy of STI-5656 in subjects with severe COVID-19

3.1.2. Secondary Objectives

To assess the safety and tolerability of STI-5656 in subjects with severe COVID-19

To assess pharmacokinetics in the study population.

3.2. Endpoints

3.2.1. Primary Endpoint

- Proportion of subjects alive and free of respiratory failure at Day 28

Respiratory failure, is defined based on resource utilization of any of the following modalities:

- Noninvasive positive pressure ventilation or continuous positive airway pressure
- Endotracheal intubation and mechanical ventilation
- Oxygen delivered by high-flow nasal cannula (heated, humidified, oxygen delivered via reinforced nasal cannula at flow rates >20 L/min with fraction of delivered oxygen ≥ 0.5)
- Extracorporeal membrane oxygenation

3.2.2. Secondary Endpoints

- Types, frequencies, and severities of AEs and the relationships of AEs to IP; includes serious adverse events SAEs
- Proportion of subjects alive and free of respiratory failure at Day 60
- Change in clinical status (on a 0-8-point ordinal scale²) of subject at Day 7, Day 14, and Day 28
- Proportion of subjects alive and discharged from ICU at Days 14 and 28

² 8-category ordinal scale of patient health status ranges: 0=no clinical or virological evidence of infection; 1=no limitation of activities; 2=limitation of activities; 3=hospitalized, no oxygen therapy; 4=oxygen by mask or nasal prongs; 5=non-invasive ventilation or high-flow oxygen; 6=intubation and mechanical ventilation; 7=ventilation + additional organ support – pressors, rapid response team (RRT), extracorporeal membrane oxygenation (ECMO); 8=death.

- Time from randomization to first occurrence of respiratory failure or death on study due to any cause up to Day 28
- Percent change from baseline in CRP at Days 3, 5, 7, 10, 14, 28
- Relative change from baseline in oxygenation index (PaO₂/FiO₂) up to Day 5
- All-cause mortality at Day 60 and Day 90
- Number of days alive and free of respiratory failure at Day 28
- Number of days with respiratory failure up to Day 28
- Number of days hospitalized up to Day 28
- Number of days in ICU (length of stay) up to Day 90
- Number of days alive outside of hospital up to Day 28
- Number of days alive outside of hospital up to Day 90
- To assess the pharmacokinetic profile in the study population

3.2.3. Exploratory Endpoints

- Change from baseline in absolute lymphocyte counts at Days 3, 5, 7, 10, 14, 28
- Change from baseline in ferritin at Days 3, 5, 7, 10, 14, 28
- Change from baseline in VEGF-A at Days 3, 5, 7, 10, 14, 28
- Change from baseline for inflammatory cytokines (IL-6, TNF- α , IFN γ , IL1 β , IL-7, IL-8, IL-10, IL-12, IL-17, IL-18, IP-10) at Days 3, 5, 7, 10, and 28

